**Figure 2: National model for telehealth in Scotland**

Source: Scottish Centre for Telehealth & Telecare (2017, s. 20), modified in The Norwegian Directorate of Health (2017, s. 10)

### 3.2 Exclusion criteria

Patients who are not competent to consent are excluded from participating in the trial. This means that patients who participate in the trial must be able to make their own decisions and understand the consequences of their

own choices. A person who is competent to consent can reason and evaluate alternatives, can express credible choices and understand the consequences of their own choices.

Other exclusion criteria include:

- Patients who are unable to handle the tablet and the measuring equipment to be used
- Patients with substance abuse; this patient group is often unstable, and telehealth is likely more applicable for patients who are likely to use the tablet and any measuring devices regularly and as intended.

### 3.3 The number of participants

The Norwegian Directorate of Health has defined a target number of participants at a minimum of 600 patients.

### 3.4 Recruitment of patients

Anybody, including health and care personnel, the patients themselves and their relatives can suggest patients for participation in the trial. In most cases, health personnel recruit patients. Suggestions are made to the project administration, which consists of municipality employees.

The Norwegian Directorate of Health has stressed that it is important that the participating municipalities focus on recruiting patients. All participating municipalities have written plans for recruitment that are regularly evaluated and updated. Among actions that are undertaken to promote recruitment of patients are information meeting at hospitals and GP offices, newspaper articles and the like.

## 4. Treatment – telehealth vs. standard clinical care

### 4.1 Telehealth

#### Organization and responsibilities

The Norwegian Directorate of Health has outlined guidelines on how to organize telehealth in clinical practice, yet the participating municipalities may adapt the service according to local needs (within the guidelines). The local centers are responsible for facilitating cooperation between the general practitioner scheme, the follow-up service and the municipalities' other health and care services. The centers are also responsible for equipment, technological solutions and telehealth software. This includes the procurement, logistics, training in the use of equipment and user support. Four different suppliers of technological solutions are involved in the trial, and consequently, technological solutions may vary across the municipalities. In addition, the centers may differ in their target population (with respect to main diagnoses), main recruitment channels, and the design of the service itself. For example, the follow-up service may have different opening hours or different physical location (e.g. at the emergency room or at the home nursing care unit).

#### Patient follow-up

Once it has been decided that a patient will receive telehealth, the GP should, together with the patient, nurse and possibly other health personnel, prepare a follow-up plan based on the patient's goals, disease burden and risk of deterioration. The Norwegian Directorate of Health, in collaboration with the participating centers are currently developing standardized follow-up plans.

Once the follow-up plan has been outlined, the user receives a tablet and potentially measuring instruments. The user is offered training in how to use the equipment. The tablet is used to answer simple questions about the patient's own health and/or perform measurements related to health status (such as blood pressure, blood sugar, oxygen saturation, weight). The registered results are automatically transferred from the measuring devices to the tablet so that user can see them and track their own results over time. The results are also automatically transmitted digitally to the follow-up service, which contacts the user in case of abnormal results.

Patients receiving telehealth will receive follow-up from a nurse at the follow-up service. The nurse monitors the user's measurements and provide medical support and guidance based on the user's needs. The nurse will respond

---

 Centers involved in the pilot study with multidisciplinary care teams may engage the same nurses in follow-up of patients receiving care from both multidisciplinary care teams and telehealth follow-up.

to abnormal results, and will, in consultation with the patient, consider whether the user should contact the GP or the emergency room.

The health personnel will, in consultation with the user, determine how often the user should carry out the measurements. For most user's, the frequency of the measurements will be gradually reduced over time. Different health conditions and diagnoses will require different follow-up; thus, the frequency of measurements will vary across users. The frequency of measurements will be recorded.

The technological solutions will inform the patient and the follow-up center when the measurement results deviate from the normal values for the user. The threshold values for when measurements are considered abnormal are dynamic and defined in consultation between the health personnel and the user. The notifications are illustrated by red, yellow or green, and the employees in the follow-up service act based on previous measurements from the user, threshold values and / or the user's perception of their own health that day. If a user does not perform the scheduled measurements, this can also cause the follow-up service to contact the user.

## 4.2 Standard clinical care

Patients who are assigned to the control group will receive standard clinical care. Exactly what kind of care they will receive depends on their illness and their needs.

# 5. Recruitment of study participants

Potential participants are first proposed by health personnel at hospitals or in municipal health and care services, by GPs, by patients themselves or their relatives, either directly to the patient's GP or to the project administration (possibly via the municipal allocation office) (step 1 in Figure 3). Participation proposals are forwarded from the project administration to the GP. Then, the GP, who has the medical responsibility for the patients on their patient list (i.e., within the GP scheme), is responsible for deciding whether the patient is eligible for receiving telehealth (step 2). In cases where the GP receives proposals directly, the GP makes this assessment immediately. If a patient is considered eligible, the patient is invited to an information meeting with a project employee where the patient is offered the opportunity to participate in the trial (step 3). If the patient gives her consent to participate in the trial, the patient is randomized into an intervention or a control group (step 4). Randomization takes place in connection with the information meeting, and the project administration is responsible for the randomization. Thereafter, the patient receives further follow-up depending on which group they are allocated to (step 5).

**Figure 3: Recruitment in the randomized control trial of telehealth**

## 5.1 Step 1: Potential participants are proposed for the trial

Both patients themselves, relatives, general practitioners and health care personnel at hospitals or in the municipal health and care service may propose relevant patients for the trial of telehealth. If the patient himself proposes to participate, the procedure will be adapted depending on where the patient first approaches his / her desire for participation (see below). Patients who are proposed as study participants will be informed that the trial of telehealth is carried out as a randomized-controlled trial.

### Recruitment via health personnel in hospitals or in municipal health and care services

Health personnel (of any type) in the specialist health service or in the municipal health and care service may propose patients for the trial. Health personnel who recruit patients should be familiar with the inclusion criteria. The health personnel may conduct an informal, introductory conversation with relevant patients and inform about

 By municipal allocation office, we mean the unit in the municipality that makes decisions about which municipal services are to be granted.

telehealth and the related trial (including the recruitment process and follow-up). The conversation will form the basis for an assessment of the patient's interest and motivation for participating in the trial, as well as the prerequisites for using simple technology. The patient must (orally) consent to being proposed for participation in the trial. Health personnel make an overall assessment of eligibility based on the conversation with the patient and, if deemed eligible, send a proposal for participation in the trial. The proposal is sent to the patient's GP or the center's administration (depending on how the local organization of the service). Such a notification constitutes an important part of the decision-making basis for the GP who decides whether the patient is suitable for participation in the trial. The message should be concise and contain information about the patient's state of health, suitability for telehealth, and motivation, as well as confirmation that the patient is informed about the trial. The centers prepare routines for how the message is transmitted from health personnel to the GP, to ensure the patient's safety and privacy.

#### **Recruitment via the general practitioner**

GPs who participate in the trial assess which patients on their list can benefit from the use of telehealth, based on their own knowledge of the patients. In the face of patients who are suitable for telehealth, the GP can discuss the items as described above (in the section "Recruitment via health professionals in hospitals or in municipal health and care services") with the patient and then report the patient to the project administration.

#### **Self-recruitment or recruitment through relatives / acquaintances**

Patients and their relatives may suggest themselves as participants in the trial. This may occur if the patient for example hears about medical distance monitoring via acquaintances, reads about it in the newspaper or the like. These patients can contact the GP, the health personnel in the municipality or the specialist health service to get in touch with the project administration.

### **5.2 Step 2: The GP assesses eligibility**

The Norwegian Directorate of Health has planned that approximately 100 GPs will participate in the trial. The centers have signed letters of intent with GPs who are committed to recruiting patients for the trial. The GP has the medical responsibility for the patients on their list and should therefore assess the patient's eligibility for telehealth (i.e., whether the patient meets the inclusion criteria) based on their knowledge of the patient, patient records and the information in the proposal message from the project administration or other health personnel.

#### **Practitioners who are not informed about the trial**

Some patients, who are recruited from hospitals, home care services or others, may have a GP who is not involved in the trial (and thus did not sign a letter of intent). These GPs may not be familiar with the trial. In these cases, the project administration will inform the GPs about the trial. These GPs can recruit patients to the trial on the same basis as GPs who have been involved from the start of the trial.

### **5.3 Step 3: Patients are invited to participate in the trial**

Patients who have been deemed eligible for participation by the GP will be contacted by the project administration and invited to an individual meeting where the patient is invited to participate in the trial. The information meeting can be held at the project employee's workplace, or at the patient's home if necessary due to the patient's health condition. At the information meeting, the project employee will inform the patient about the trial and about telehealth. The meeting will include:

- Information about the trial and what participation means for the patient. The Norwegian Directorate of Health and the centers have prepared information material (a brochure and an information film) that can be used as a basis for the discussion.
- Obtaining consent for participation (see details below)
- Completion of a questionnaire about her physical and mental health, follow-up from and experiences with the health and care service, and background information, including demographics, marital status, place of residence and housing, scope of informal care from family and friends, use of other types of welfare technology (security alarm, self-help tools, etc.).
- Randomization into intervention or control group (see section 5.4)
- Information on further follow-up (see section 5.5)

### Obtaining consent for participation

After the project employee has informed the patient about the trial and what the participation entails, the patient is asked whether he / she agrees to participate in the trial. If the patient agrees to participate in the trial, the patient signs the consent form. A requirement for participation is that the patient is competent for consent. Relatives cannot consent on behalf of the patient. The patient cannot receive telehealth without the consent to participate in the trial.

If the patient does not agree to participate in the trial, the meeting ends, and the patient is followed up further by the healthcare service according to standard clinical care. In this case, the patient will not be able to receive telehealth, and patient information is not recorded as part of the trial. However, anonymous information is registered to inform the analysis of loss-to-follow-up (see section 9.5). If the patient does not agree to participate in the trial, the randomization envelope is not opened, and the project employee brings the unopened envelope back to the office and place it back in the stack of envelopes.

If the patient needs more time before he / she decides whether to participate or not, the patient may have a reflection period of a maximum of two weeks. Equipment for the use of telehealth cannot be delivered to the patient before the patient has signed the consent statement for participation in research.

## 5.4 Step 4: Consenting patients are randomized

Patients who agree to participate in the trial sign the consent form before the randomization process. Once the patient has signed the consent form and completed the baseline questionnaire, the patient and the project employee open the randomization envelope together. The project employee informs the patient about the outcome of the randomization and explains how the follow-up will be organized (described in more detail in chapter 5.5). The meeting ends, and the project employee ensures that the patient is followed up in accordance with the protocol according to assigned treatment group (i.e., intervention / control).

Participants in the control group may, after the end of the follow-up period, receive a new assessment of the use of telehealth. Participants who withdraw their consent will be able to receive a new assessment no earlier than one year after the consent is first signed.

## 5.5 Step 5: Assessments of participants

### Assessments the intervention group

How telehealth will be delivered will vary between both centers and individual patients. During the information meeting, the patients are informed of what is expected from them in connection with the evaluation of the trial (Table 2). Participants in the intervention group will be asked to complete a questionnaire every six months during the follow-up period, which lasts up to 18 months. The first questionnaire is completed at the information meeting. The questionnaires are distributed by mail.

Some users (and their relatives) will be requested to be interviewed one or two times during the project period. In addition to questionnaires and interviews, we collect information about the patients from various administrative registries, including the use of health and care services within municipal health and care services, the fixed-care service and the specialist health service. Details of the registry data are described in Table 3.

**Table 2: Assessments of participants in the trial**

	Intervention group	Control group
Questionnaire	

Survey every six months for 18 months

The collection of survey information is terminated in June 2021

	

Survey every 6th month for 18 months

The collection of survey information is terminated in June 2021

Interviews	

Selected participants are interviewed once or twice during the follow-up period

	

None

Registry data	

Registry data are collected for the period 2017-2022

	

Registry data are collected for the period 2017-2022

---

Patient data from the follow-up service	

• Data on measurements are collected if the patient uses telehealth

• The collection of information is terminated in June 2021

	

• None

--	--	--

---

### Assessments in the control group

Patients included in the control group receive regular follow-up from the health service. They are informed that they are expected to participate in the trial by completing a questionnaire every six months during the follow-up period, which lasts for up to 18 months or until the patient withdraws their consent for participation. The first questionnaire is filled out at the information meeting. The following questionnaire is distributed by mail. We will collect registry data for the participants in the control group (corresponding register data for the participants in the intervention group). After the follow-up period, participants in the control group may receive a new assessment related to telehealth.

## 5.6 After the follow-up period

After completing the 18-month follow-up period, the participants can have a new the assessment of eligibility for the use of telehealth if the municipality continues the service. If a patient in the intervention group still receives telehealth, we will continue to record information from the follow-up service unless the patient does not consent to this. We will collect this information until June 30, 2021.

We will obtain registry data information covering all participants in the period 2017-2022. We collect data after the follow-up period to allow potential analyses of longer-term effects.

## 5.7 Withdrawal from the intervention and/or the trial

Patients may withdraw from receiving telehealth at any time during the study period, without reasoning, by contacting the local project administration. Study participants may withdraw from the trial with or without withdrawing their consent to participate. If a participant withdraws from the trial and withdraws the consent, collected information about the patient will be deleted and no additional information will be collected. If the patient withdraws without withdrawing their consent, collected information will be stored and used in the evaluation. The patient will be asked if he/she is willing to participate in the evaluation through questionnaires or interviews. The patient will also be asked if registry data can be collected until the end of the project period.

The municipality is responsible for following up patients who are withdrawing from the trial.

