## 9.2 Randomization

Patients who agree to participate in the trial are randomized 1: 1 to the intervention and control group. The treatment allocation is non-blinded in that both providers and patients will know the outcome of the treatment allocation. The actual randomization is carried out by a project employee in the local centers. The project administration stores sealed randomization envelopes in their office. Each sealed envelope contains a sheet marked with either "tiltak" (intervention) or "kontroll" (control), which determines which group the patient is placed in. For each GP in the trial, there is a separate stack of six envelopes: three "intervention" and three "control". Each time a patient on GP's X's list is invited to an information meeting, the project employee takes the top envelope from GP's stack of envelopes. If more than six patients are recruited on the GP's patient list, the project employee will receive a new stack of six envelopes for this GP. Thus, we can ensure that there will be approximately equal distribution of intervention and control patients from each GP. Oslo Economics distributes the stacks of opaque envelopes to the projects.

If a patient is invited to an information meeting and the patient's GP has not previously been involved in the trial, a separate stack of envelopes for this GP should be obtained prior to the meeting so that the patient can be randomized into the trial.

For each information meeting (chapter 8.3), the project employee takes an envelope from the appropriate GP's stack *without opening it*. The envelope is opened together with the patient after the consent form is signed, and the questionnaire is filled out. If the patient does not agree to participate in the trial, the envelope remains sealed. The project employee brings the sealed envelope back to the office and puts it back in the proper stack of envelopes.

 This randomization technique was considered the best practically implementable technique given the practical implementation of the study.

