## 9.3 Sample for analysis

We will study the following range of patients:

- Intention to treat (ITT) population: this is the sample of randomized patients, regardless of whether they are followed up using telehealth or not
- Per-protocol (PP) population: this is the sub-sample of the ITT population that follows the study protocol during the entire follow-up period (12-18 months)
- Safety population: this is the subset of the ITT population that begins follow-up (uses telehealth), and either completes follow-up or withdraws from the study.

The analysis will mainly be carried out using the ITT population. The reason for this is that loss-to-follow-up is likely to bias the results so that we estimate a greater effect of the use of telehealth than what is estimated by focusing on the PP population. Thus, an analysis of the ITT population is a more conservative estimate.

In addition, we will carry out analyses where we compare the outcome of the intervention group with one or more registry-based control groups. The control groups can be selected based on discretionary assessments and / or by means of statistical methods, e.g. propensity score matching. It will be possible to base the choice of control group on variables such as gender, age, diagnosis and municipality of residence. The results of such an analysis will have to be interpreted with caution but will constitute an interesting supplement to the rest of the analysis.

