## 9.5 Analysis of loss-to-follow-up

We expect loss-to-follow-up among the participants in the ITT population, and it is important to document this in order to be able to interpret the results. Patients can drop out either before or after consent is given.

We will register anonymous information about patients who drop out before consent is given. This includes gender, age (in intervals), main diagnosis, recruitment channel, reason for non-participation.

Drop-out that occur after the consent has been obtained will be analyzed to ensure that drop-out does not drive the results. Characteristics of those who drop out will be compared to those who complete the follow-up.

Drop out will also be highlighted through interviews with GPs and other health personnel, as well as with the project administration.

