## 12.2 Informed consent procedure

The research group and/or the project administration is responsible for giving the patients full and adequate verbal and written information about the nature, purpose, risk and benefits of the trial. They are informed about the strict confidentiality of their patient data, but that their medical records may be reviewed by the researchers for evaluation purposes.

It is emphasized that the participation is voluntary and that the patient can refuse further participation in the trial whenever she/he wants. This will not prejudice the patient's subsequent care. Participants who withdraw their consent may request that all information collected be deleted, unless they are included in publications or articles.

Patients who have not signed the written consent form cannot obtain equipment from the municipality, and consent is thus a prerequisite for participation in the trial. The consent form is enclosed in Appendix A.

A copy of the signed consent statement is given to the patient. Signed consent statements are collected in a suitable folder by the project administration and will also be scanned and stored electronically at the project administration.

Written consent will be also obtained from participants in the evaluation other than those in the intervention and control group. This includes interviewees, such as GPs, employees and the follow-up service, other representatives from the health and care service and relatives.

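### Sections 5.7 and 12.2 contradict each other on deleting a consent-withdrawer's data, which can take randomised patients out of the ITT analysis, and the section 9.3 safety population has no controls

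*Combined protocol and SAP*

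**What the plan says.** **Deletion.** Section 5.7 sets an automatic rule: "If a participant withdraws from the trial and withdraws the consent, collected information about the patient will be deleted". It adds that nothing more is collected. Leaving while keeping consent is treated differently: "If the patient withdraws without withdrawing their consent, collected information will be stored and used in the evaluation". Section 12.2 gives another rule for consent-withdrawers: "Participants who withdraw their consent may request that all information collected be deleted, unless they are included in publications or articles".

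**Analysis sets.** Section 9.3 defines the ITT population: "this is the sample of randomized patients, regardless of whether they are followed up using telehealth or not". It makes this the main analysis set, on the ground that "loss-to-follow-up is likely to bias the results so that we estimate a greater effect of the use of telehealth". The comparison with the per-protocol set in that sentence is worded unclearly, but ITT is plainly meant as the conservative choice. Section 9.5 plans a drop-out analysis: "Characteristics of those who drop out will be compared to those who complete the follow-up".

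**Safety.** Section 9.3 defines the safety population: "this is the subset of the ITT population that begins follow-up (uses telehealth), and either completes follow-up or withdraws from the study". The synopsis lists recording of adverse events as a safety assessment, and section 7 makes the local centres responsible for finding and documenting them. Neither limits this to telehealth users.

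**The concern.** A centre cannot follow both 5.7 and 12.2 when a participant withdraws consent and says nothing about deletion. Section 5.4 has consent signed before the envelope is opened, so later consent-withdrawers are normally randomised patients. If their data are erased, the analysis is no longer of everyone randomised, and section 9.5 cannot compare their characteristics with those of completers. This matters because 9.3 relies on the ITT set as protection against bias from loss to follow-up.

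Balanced loss between arms cannot be taken for granted. Allocation is open, and wanting to use telehealth is an inclusion criterion. Under 5.4, controls may be reassessed for telehealth after follow-up (up to 18 months), while consent-withdrawers may be reassessed from one year after signing.

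The safety population raises a separate problem. In chronically ill patients, a count of events among telehealth users alone cannot show whether events are more or less frequent than under standard care.

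**Working it through.** **1. The deletion rules, case by case**

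| Randomised patient | Section 5.7 | Section 12.2 | In ITT analysis and 9.5 comparison? |
|---|---|---|---|
| Stops, keeps consent | Kept and used | Not addressed | Yes, with the data held |
| Withdraws consent, asks for deletion | Deleted | Deleted, except published data | No |
| Withdraws consent, makes no request | Deleted | Not deleted | 5.7: no. 12.2: not stated |

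The conflict lies in the third row and in the publication exception. Section 12.2 does not say that undeleted data will be analysed, so neither section settles the ITT status of these patients. Sections 9.3 and 9.5 do not mention them.

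**2. Size**

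Inputs: 600 patients planned, 1:1 (synopsis, 9.2), so 600 / 2 = 300 per arm. Every 3 erased patients are 3 / 300 = 1% of an arm. The documents give no consent-withdrawal rate, so anything further is assumption.

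*Precision.* Table 7, panel A, is reproduced first: n per arm = 2 × (1.96 + 0.842)² × 0.238² / 0.05² = 356, as stated (two-sided 5%, 80% power). With 300 per arm, power for a VAS difference of 0.05 is 73.0%. If 5%, 10% or 20% of both arms were erased (285, 270 or 240 left per arm), it would be 70.8%, 68.5% or 63.4%.

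*Bias.* Suppose a fraction f of one arm is erased and those patients' mean is lower by g than the mean of the retained patients. The retained mean then exceeds the full-arm mean by f × g.

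| f (assumed) | g = 0.05 | g = 0.10 | g = 0.20 |
|---|---|---|---|
| 5% | 0.0025 | 0.005 | 0.01 |
| 10% | 0.005 | 0.01 | 0.02 |
| 20% | 0.01 | 0.02 | 0.04 |

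Against the 0.05 difference in Table 7, this runs from 0.0025 / 0.05 = 5% to 0.04 / 0.05 = 80%. The width of that range is the finding: the documents do not allow a narrower one.

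**3. Who is in the safety population under 9.3**

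- Starts telehealth, then completes or withdraws: in.
- Starts telehealth, then dies: unclear. The definition names only completion and withdrawal, and section 6.1 describes a fairly old and ill population.
- Allocated to telehealth but never starts: out.
- Control treated as allocated: out, so 0 of about 300.

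**4. What exists in both arms.** Section 5.5 collects register data for controls as for the intervention group. Section 6.3 plans emergency-service contacts and admissions for all participants. A between-arm comparison is therefore feasible, but 9.3 does not tie the safety population to it. Table 3 names no register for deaths; section 5.9 leaves the list of registers open.

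**The case against.** **On deletion.** Both sections provide for deletion, and 12.2 could be read as a summary of a right rather than as an operating rule. The consent form (Appendix A) was not available here and may fix which rule applies. That stands as a limit on the remedy, but 5.7 and 12.2 would still need aligning with each other.

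The affected group may be small, because 5.7 keeps everyone who stops without withdrawing consent. That stands too.

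A reader might infer that erased patients disappear even from the counts. The documents do not support this. Under 8.2 the eCRF records consent, allocated group, termination date and the reason for any interruption. Under 12.3 the project administration lists everyone who signed consent. Nothing says that deletion reaches those records, although nothing exempts them either. Section 9.5 also explores drop-out through interviews.

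**On safety.** Table 1 contains no safety objective or endpoint, and 9.3 promises no between-arm safety comparison. A reader might infer that harms go uncompared altogether, but emergency contacts and admissions are already planned in both arms under 6.3. What stands against the plan is narrower: the set it labels as the safety population cannot support a comparison, although adverse events are not restricted to one arm.

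It is also tempting to say that detection is more intensive under telehealth. Section 7 gives no detection method for either arm, so the documents support only that it may differ, because nurses follow telehealth users (4.1).

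**Conclusion.** The contradiction between 5.7 and 12.2 is certain on the text. Followed as written, 5.7 removes randomised consent-withdrawers from the ITT analysis and from the 9.5 comparison. How many, and with what effect, is unknown. The power and bias figures above rest on assumed rates and gaps and are not evidence about this trial. A reader might infer that the ITT result is biased, or that controls are the ones who will be lost. The documents give reasons not to assume balance, but no rate and no sign of the direction.

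The 9.3 safety population excludes every control treated as allocated and leaves deaths unclear, so it cannot show whether events are more or less frequent than under standard care.

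Both points should be corrected. Confidence is medium, because the consent form could settle the first and the plan claims no comparative safety objective for the second.

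**What to change.** **Deletion**

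- Reconcile 5.7, 12.2 and the consent form into one rule.
- Where the consent and data-protection terms allow, keep data collected before withdrawal and include them in the ITT analysis unless the participant asks for deletion. If the terms require automatic deletion, say so in 9.3 and 9.5.
- In either case, report numbers randomised, withdrawn and erased by arm from the allocation and consent records (8.2, 12.3), as far as those may be kept. There is no need to reconstruct allocation from the stacks described in 9.2 ("For each GP in the trial, there is a separate stack of six envelopes"), which would mean opening sealed opaque envelopes.

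**Safety**

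- Define the safety set in 9.3 as all randomised patients in both arms, including those who die.
- Base the between-arm comparison on the 6.3 register outcomes: emergency contacts and admissions.
- Report centre-recorded adverse events by arm descriptively, noting that detection may differ between arms.
- Name the source for deaths in both arms.

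**Cost.** The cost is protocol wording, a check against the consent and data-protection terms, and a small extra analysis of data already planned. Register outcomes miss events that lead to no recorded contact. The telehealth nurse may prompt emergency contacts (4.1), so that outcome can move for reasons other than harm. A source for deaths may have to be added.
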